1.3 Number of Subjects

The sample size for this study was selected to be consistent with the research hypothesis as described in Section 1.2 of the CSP.

The two co-primary endpoints of this study are OS and PFS. To control for type-I error, a significance level of 2.5% will be used for analysis of OS and a significance level of 2.5% will be used for analysis of PFS. The study will be considered positive (a success) if either the PFS analysis results and/or the OS analysis results are statistically significant.

Approximately 702 patients will be randomised 2:1 to obtain 491 death events in the ITT population (70% maturity). The primary PFS analysis DCO will occur when it is expected that 458 PFS events have occurred (65% maturity). If the true PFS HR is 0.67, the study will provide at least 95% power to demonstrate a statistically significant difference for PFS with a 2-sided significance level of 2.5% in the ITT population; this translates to a 5-month benefit in median PFS over 10 months on placebo if PFS is exponentially distributed. The smallest treatment difference that would be statistically significant is a HR of 0.8. A recruitment period of approximately 22 months and a follow-up period of 14 months are expected for the PFS endpoint. Therefore it is anticipated that this PFS analysis could be performed approximately 36 months after the first patient has been randomised.

The primary OS analysis DCO will occur when it is expected that 491 OS events have occurred (70% maturity). If the true OS HR is 0.73, this number of death events will provide at least 85% power to demonstrate a statistically significant difference for OS, assuming a 2.5% 2-sided significance level in the ITT population; this translates to an 8-month benefit in median OS over 22 months on placebo if OS is exponentially distributed (Butts et al 2014). The smallest treatment difference that would be statistically significant is a HR of 0.81. A recruitment period of approximately 22 months and a follow-up period of 40 months are expected for the OS endpoint. Therefore it is anticipated that this OS analysis could be performed at approximately 62 months after the first patient has been randomised.

2. ANALYSIS SETS

2.1 Definition of Analysis Sets

Four main analysis sets are defined for this study.

Full analysis set (FAS) (Intention to treat (ITT)):

The primary statistical analysis of the efficacy of MEDI4736 vs placebo will include all randomised patients and will compare the treatment arms on the basis of randomised treatment, regardless of the treatment actually received. Patients who were randomised but did not subsequently go on to receive study drug are included in the ITT population. Note, this is also known as the FAS. Therefore, all efficacy and HRQoL data will be analysed using the FAS on an ITT basis.

Safety analysis set:

All patients who received at least one dose of randomised study medication, MEDI4736 or placebo, (regardless of whether that was the randomised therapy intended or indeed whether, in rare cases, they received therapy without being randomised) will be included in the safety population. Throughout the safety sections, erroneously treated patients (e.g., those randomised to Treatment A but actually given Treatment B) will be accounted for by the actual treatment administered. As long as a patient received any dose of MEDI4736, the patient would be counted under MEDI4736 treatment group.

When assessing safety and tolerability, summaries will be produced based on the safety analysis set.

PK analysis set:

All patients who receive at least 1 dose of MEDI4736 per the protocol, for whom any post-dose data are available and do not violate or deviate from the protocol in ways that would significantly affect the PK analyses will be included in the PK analysis set. The population will be defined by the Study Team Physician, Pharmacokineticist and Statistician prior to any analyses being performed.

Table 1 gives a summary of outcome variables and analysis populations.

Table 1 Summary of outcome variables and analysis populations

Outcome variable	Populations
Efficacy Data	
OS (co-primary)	FAS (ITT)
PFS (co-primary)	FAS (ITT)
OS24, APF12, APF18, PFS2, DoR, TTDM, TFST, PRO endpoints, World Health Organisation performance status	FAS (ITT)
ORR	FAS (ITT)
Study Population/Demography Data	
Demography characteristics (e.g. age, sex etc.)	FAS (ITT)
Baseline, disease characteristics	FAS (ITT)
Analysis populations	FAS (ITT)
Important deviations	FAS (ITT)
Medical/Surgical history	FAS (ITT)
Previous anti-cancer therapy	FAS (ITT)
Concomitant medications/procedures	FAS (ITT)
Subsequent anti-cancer therapy	FAS (ITT)
World Health Organization performance status	FAS (ITT)

Table 1 Summary of outcome variables and analysis populations

Outcome variable	Populations
PK Data	
PK data	PK
Immunogenicity	
Immunogenicity data	Safety
Safety Data	
Exposure	Safety
Adverse events	Safety
Laboratory measurements	Safety
Vital Signs	Safety
ECGs	Safety

APF12 Proportion of patients alive and progression free at 12 months from randomisation; APF18 Proportion of patients alive and progression free at 18 months from randomisation; DoR Duration of response;; ITT Intent-to-Treat; ORR Objective response rate; OS Overall survival; OS24 Proportion of patients alive at 24 months from randomisation; PFS Progression free survival; PFS2 Time from randomisation to second progression; PK Pharmacokinetic; PRO Patient reported outcomes; TTDM Time to death or distant metastasis, TFST Time to first subsequent therapy or death.

2.2 Protocol Deviations

The important protocol deviations will be listed and summarised by randomised treatment group. Deviation 1 below will lead to exclusion from the Safety analysis set. This means that this will not be shown on the relevant summary but can still be identified on the listings. None of the other deviations will lead to any patient being excluded from any of the analysis sets described in Section 2.1 (with the exception of the PK analysis set, if the deviation is considered to impact upon PK). If the deviations are serious enough to have the potential to impact the primary analysis, sensitivity analyses may be performed. The need for such a sensitivity analysis will be determined following review of the protocol deviations ahead of database lock (DBL) and will be documented prior to the primary analysis being conducted. Eligibility criteria deviations are deviations from the protocol inclusion and exclusion criteria. Post-entry deviations are deviations from the protocol that occurred after the patient was assigned to the study treatment.

The following general categories will be considered important deviations and be listed and discussed in the CSR as appropriate for the study:

- Deviation 1: Patients randomised but who did not receive MEDI4736/matching placebo
- Deviation 2: Patients who deviate from the following key entry criteria in CSP Amendment:
 - a) Inclusion criteria: 3, 4, 5, 8

b) Exclusion criteria: 5, 6, 7, 8, 10, 12, 13, 14, 17

- Deviation 3: Baseline RECIST scan > 42 days before randomisation.
- Deviation 4: No baseline RECIST 1.1 assessment on or before date of randomisation.
- Deviation 5: Received prohibited concomitant systemic anti-cancer agents.

Refer to the CSP section 5.6 for those medications that are detailed as being ‘excluded’ from permitted use during the study. This will be used as a guiding principle for the physician review of all medications prior to DBL.

- Deviation 6: Patients randomised who received treatment other than that to which they were randomised to.

The categorisation of these as important deviations is not automatic and will depend on duration and the perceived effect on efficacy.

In addition to the programmatic determination of the deviations above, monitoring notes or summaries will be reviewed to determine any important post entry deviations that are not identifiable via programming, and to check that those identified via programming are correctly classified. The final classification will be made at the blind data review meeting (BDRM) prior to DBL or DCO. Decisions made at the BDRM will be documented and approved by AstraZeneca prior to analysis.

Errors in treatment dispensing, in addition to incorrect stratifications, will also be investigated more closely. This may occur when a patient is not randomised or treated according to the randomisation schedule on at least one occasion. It is envisaged that there will be 3 sub categories of this within the important deviations summary:

- Patients who receive no treatment whatsoever for a period of time due to errors in dispensing of medication. Note, this is not due to tolerability issues where patients may stop taking drug.
- The patient receives a treatment pack with a different code to their randomisation code and the treatment differs from the randomized treatment.
- The patient receives a treatment pack with a different code to their randomisation code. However, the actual treatment may still match the randomised treatment. For example, a patient is given randomisation code 0001, which according to the randomisation schedule is MEDI4736. However, at the randomisation visit they are given treatment pack 0003, but this still contains MEDI4736.

Patients who receive the wrong treatment at any time will be included in the safety analysis set as described in Section 2.1. During the study, decisions on how to handle errors in treatment dispensing (with regards to continuation/discontinuation of study treatment or, if

applicable, analytically) will be made on an individual basis with written instruction from the study team leader and/or statistician.

3. PRIMARY, SECONDARY AND EXPLORATORY VARIABLES

3.1 Derivation of RECIST Visit Responses

For all patients, the RECIST version 1.1 (see further Appendix F of the CSP and Independent Review Charter) tumour response data will be used to determine each patient's visit response. It will also be used to determine if and when a patient has progressed and also their best objective response.

The baseline tumour assessment is part of the screening procedures and should be performed within 0 to 42 days after the end of chemoradiation therapy and no more than 28 days before the start of study drug. For patients who are recovering from toxicities associated with prior treatment, randomisation may be delayed by up to 42 days from the end of the chemoradiation therapy.

Efficacy for all patients will be assessed by objective tumour assessments every 8 weeks (relative to the date of randomisation) for the first 12 months, then every 12 weeks thereafter, until confirmed objective disease progression as defined by RECIST 1.1 (irrespective of the reason for stopping study drug and/or subsequent therapy). For patients who discontinue study drug due to toxicity or a reason other than confirmed PD, objective tumour assessments should be continued every 8 weeks for 48 weeks (relative to the date of randomisation) then every 12 weeks thereafter until confirmed objective disease progression. If an unscheduled assessment is performed, and the patient has not progressed, every attempt should be made to perform the subsequent assessments at their scheduled visits.

Disease progression requires confirmation, the confirmatory scan should occur preferably at the next scheduled visit and no earlier than 4 weeks after the initial assessment of PD in the absence of clinically significant deterioration. Study treatment will continue between the initial assessment of progression and confirmation for progression. For all patients who are treated through progression and patients who achieve disease control (i.e., CR, PR or SD) through to the end of the 12 month treatment period and restart study treatment upon evidence of PD (according to RECIST 1.1), with or without confirmation, during follow-up, the investigator should ensure patients do not have any significant, unacceptable or irreversible toxicities that indicate continuing treatment will not further benefit the patient, and that the patient still meets all of the inclusion criteria and none of the exclusion criteria for this study including re-consenting to continue or restart treatment. To restart study treatment the patient must not have received an intervening systemic anti-cancer therapy post study drug discontinuation. Study drug should be discontinued if there is confirmed PD following a previous response (PR or CR) to study drug.

Patients with rapid tumour progression or with symptomatic progression that requires urgent medical intervention (eg, central nervous system metastasis, respiratory failure due to tumour compression, spinal cord compression) will not be eligible to continue to receive study drug.

Progression would be considered confirmed if the following criteria are met:

- $\geq 20\%$ increase in the sum diameters of target lesions (TLs) compared with the nadir at 2 consecutive visits with an absolute increase of at least 5 mm

The assessment of progression of $\geq 20\%$ increase in the sum diameters of TLs compared with the nadir is at the first progression time point relative to the nadir (the smallest sum of diameters and this may be at baseline or subsequent follow-up visit). The confirmed scan confirms the persistence of the $\geq 20\%$ increase relative to the nadir.

- and/or significant progression (worsening) of non target lesions (NTLs) or new lesions at the confirmatory PD time point compared with the first time point where progression of NTLs or new lesions identified
- and/or additional new unequivocal lesions at the confirmatory PD time point compared with the first time point new lesions identified.

BICR according to RECIST 1.1 will be regarded as primary in terms of the efficacy analyses. Sensitivity analyses will be performed using investigator assessment data and BICR using RECIST 1.1 modified for confirmation of progression. Additionally, the BICR will also be performed using irRECIST 1.1 (Wolchok et al 2009, Nishino et al 2013) Nishino et al 2013, see also Section 3.1.3) for exploratory purposes.

From the investigator's review of the imaging scans, the RECIST tumour response data will be used to determine each patient's visit response according to RECIST version 1.1. At each visit, patients will be programmatically assigned a RECIST 1.1 visit response of CR, PR, SD or PD, using the information from target lesions (TLs), non-target lesions (NTLs) and new lesions and depending on the status of their disease compared with baseline and previous assessments. If a patient has had a tumour assessment which cannot be evaluated then the patient will be assigned a visit response of not evaluable (NE) (unless there is evidence of progression in which case the response will be assigned as PD).

RECIST outcomes (i.e., PFS and ORR etc) will be calculated programmatically for the BICR and site investigator data from the overall visit responses.

3.1.1 Blinded Independent Central Review (BICR) Assessment Using RECIST 1.1

A planned BICR will be carried out using RECIST version 1.1. All radiological scans for all patients (including those at unscheduled visits, or outside visit windows) will be collected on an ongoing basis and sent to an AstraZeneca appointed Contract Research Organisation (CRO) for central analysis. Information prior radiotherapy from the CRF will also be

provided to the BICR to delineate the anatomical region of previous definitive radiotherapy, to confirm that there are no lesions at baseline outside the prior radiotherapy region, to allow the selection of appropriate target lesions, if any at baseline, and to designate new lesions at follow-up that are outside the region of prior radiotherapy as ‘distant’ metastases for derivation of TTDM. The imaging scans will be reviewed by 2 independent radiologists using RECIST 1.1 and will be adjudicated, if required (i.e. two primary reviewers review the scans and adjudication is performed by a separate reviewer in case of a disagreement). The adjudicator must choose the assessments of one of the two primary reviewers. For each patient, the BICR will define the overall visit response (ie, the response obtained overall at each visit by assessing TLs, NTLs and new lesions) data and no programmatic derivation of visit response is necessary. Possible overall visit responses include: for patients with TLs at baseline: CR, PR, SD, PD, not evaluable [NE]; for patients with NTLs at baseline only: CR, non-CR/non-PD (NN), PD or NE; for patients with no disease identified at baseline: PD, no evidence of disease [ND], NE. If a patient has had a tumour assessment that cannot be evaluated then the patient will be assigned a visit response of NE (unless there is evidence of progression in which case the response will be assigned as PD). RECIST assessments/scans contributing towards a particular visit may be performed on different dates and for the central review the date of progression for each reviewer will be provided based on the earliest of the scan dates of the component that triggered the progression.

If adjudication is performed, the records from the primary reviewer with which the adjudicator agreed will be used for data analysis (note in the case of more than one review period, the latest adjudicator decision will be used). In the absence of adjudication, the records for all visits for a single reviewer will be used. The reviewer selected in the absence of adjudication will be the reviewer who read the baseline scan first. The records from the single selected reviewer will be used to derive all BICR RECIST information including dates of progression, visit response, censoring and changes in target lesion dimensions. Endpoints (of PFS, ORR and DoR) will be derived programmatically from this information.

Results of this independent review will not be communicated to Investigators and the management of patients will be based solely upon the results of the RECIST 1.1 assessment conducted by the Investigator.

The BICR of all patients up to each DCO will be completed before the data-base lock for the interim analysis. Additionally the BICR of all patients will be performed for the final database lock for PFS which will cover all of the scans up to that point.

Further details of the BICR will be documented in the Independent Review Charter.

3.1.2 BICR assessment using RECIST 1.1 Modified for Confirmation of Progression

The BICR of all scans used in the assessment of tumours will be assessed using RECIST 1.1 modified for confirmation of progression as detailed in Sections 3.1 and 3.1.1. This means that the visit response of PD must be confirmed by another visit response of PD at the next

scheduled visit and no earlier than 4 weeks after the initial assessment of PD in the absence of clinical deterioration. Confirmation of progression needs to be programmatically derived.

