A new lesion indicates progression so the overall visit response will be PD irrespective of the TL and NTL response.

If the question ‘Any new lesions since baseline’ has not been answered with Yes or No and the new lesion details are blank this is not evidence that no new lesions are present and should be treated as NE in the derivation of overall visit response.

Symptomatic deterioration is not a descriptor for progression of NTLs: it is a reason for stopping study therapy and will not be included in any assessment of NTLs.

Patients with ‘symptomatic deterioration’ requiring discontinuation of treatment without objective evidence of disease progression at that time should continue to undergo tumour assessments where possible until objective disease progression is observed.

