Ascertainment bias will be assessed by analysing the site investigator data. The stratified log-rank test will be repeated on PFS using the site investigator data based upon RECIST. If there is an important discrepancy between the primary analysis using the BICR assessments and this sensitivity analysis using investigator assessments, then the proportion of patients with site but no central confirmation of progression will be summarised; such patients have the potential to introduce bias in the central review due to informative censoring. An approach that imputes an event at the next visit in the central review analysis may help inform the most likely HR value (Fleischer et al 2011), but only if an important discrepancy exists.

Disagreements between investigator and central reviews of RECIST progression will be presented for each treatment group. The summary will include the early discrepancy rate which is the frequency of central review declared progressions before the investigator review as a proportion of all central review progressions and the late discrepancy rate which is the frequency of central review declared progressions after the investigator review as a proportion of all discrepancies.

- Confirmation bias

An additional sensitivity analysis using the BICR data will be performed to determine the effect of confirmation of progression. The stratified log-rank test will be repeated on PFS using BICR data based upon RECIST modified for confirmation of progression. The HR and CI will be presented.

Subgroup/Additional Analysis

An exploratory analysis of PFS using the irRECIST 1.1 data provided by the BICR will be performed on the BICR analysis set. The stratified log-rank test will be repeated on PFS using the BICR based upon the irRECIST 1.1 data. The HR and CI will be presented.

Subgroup analyses and a forest plot will be generated comparing PFS between treatments in the same way as previously specified for OS. Unless there is a marked difference between the results of the statistical analyses of the PFS from the BICR data and that of the site investigator, this will only be performed upon the PFS endpoint using the BICR data based upon RECIST. No adjustment to the significance level for testing will be made since all these

subgroup and sensitivity analyses will be considered supportive of the primary analysis of PFS.

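### SAP 3.1.2 confirms progression on a second PD visit response, while the Section 3.1 criteria it cites require worsening for new-lesion and non-target PD, so the confirmation sensitivity analyses have two conflicting rules

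*SAP*

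**What the plan says.** SAP 3.1.2 covers the BICR data. It describes RECIST 1.1 as "modified for confirmation of progression as detailed in Sections 3.1 and 3.1.1". It then explains what that means: "the visit response of PD must be confirmed by another visit response of PD at the next" scheduled visit, at least four weeks after the first unless there is clinical deterioration. It adds that confirmation has to be derived by program.

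SAP 3.1, to which it points, sets criteria by type of lesion. Meeting any one is enough:

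- Target lesions: "increase in the sum diameters of target lesions (TLs) compared with the nadir at 2 consecutive visits", of at least 20% and 5 mm. Persistence suffices.
- Existing non-target lesions or new lesions: "significant progression (worsening) of non target lesions (NTLs) or new lesions at the confirmatory PD time point compared with the first time point" at which they were seen.
- Further lesions: "and/or additional new unequivocal lesions at the confirmatory PD time point compared with the first time point new lesions identified".

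Protocol Section 6.3 and Appendix F Section 5 carry the same list. SAP 3.2.1.2 and protocol 11.1.3.2, which define the confirmed-PFS variable, say only that the next scheduled scan must confirm. They give no lesion-level criterion. Both count a single PD with no later scan as progression.

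On visit responses, SAP 3.1.5, written for site reads, says: "A new lesion indicates progression so the overall visit response will be PD irrespective of the TL and NTL response". Under SAP 3.1.1 the BICR readers supply the visit response directly.

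SAP 4.2.1.2 uses the confirmed variable under the heading of confirmation bias: "An additional sensitivity analysis using the BICR data will be performed to determine the effect of confirmation of progression". SAP 3.2.2.2 and 4.2.2.2 apply the same modification to ORR.

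**The concern.** Section 3.1.2 cites one rule and writes out another. Because BICR delivers visit responses and confirmation is programmed from them, the weaker rule is the one likely to be coded. A new lesion that is still there at the next scan, neither larger nor joined by others, would normally give a second PD response and so count as confirmed. Under the cited criteria it would not.

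The protocol explains why confirmation was introduced. Section 3.2.3.4 says responses to immunotherapy may be delayed or may follow conventional PD, and that RECIST is modified to allow for this. A lesion that appears and then stays stable is one such pattern. For that pattern, agreement between the primary and confirmed analyses would be partly built in by the derivation.

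New lesions carry weight in this population. Patients with no evidence of disease at baseline may enter (Appendix F Section 2), and for them only a new lesion can produce PD (SAP 3.1.4). SAP Section 6 also expects some assessments of irradiated disease to be non-evaluable.

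Two programmers working in good faith from this SAP could produce different event sets. Table 9 of the SAP, which lists changes from the protocol, does not mention replacing the worsening criteria.

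**Working it through.** No stated figure is in dispute, so there is none to reproduce. The check sets the two rules side by side.

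**Rule A (SAP 3.1.2 as worded):** confirmed if the visit response is PD at the first scan and PD again at the next scheduled scan.

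**Rule B (SAP 3.1):** confirmed if the target-lesion increase persists, or non-target or new lesions have significantly worsened since the first PD scan, or additional unequivocal new lesions have appeared.

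| First PD and next scheduled scan | Rule A | Rule B |
|---|---|---|
| Target-lesion increase persists | confirmed | confirmed |
| Target-lesion increase falls back below 20% over nadir | not | not |
| New lesion worsens, or another appears | confirmed | confirmed |
| **New lesion persists unchanged, none added** | **confirmed** | **not** |
| New lesion gone, visit read as non-PD | not | not |
| Non-target PD worsens further | confirmed | confirmed |
| **Non-target PD persists, no further worsening** | **confirmed** | **not** |
| Non-target PD reverts to non-PD | not | not |

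The rules agree in 6 of 8 patterns and differ in 2. Both differences run the same way: Rule A confirms and Rule B does not.

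As an illustration, take a patient whose only finding at week 16 is one new lesion, unchanged at week 24. If BICR reads a persisting new lesion as PD, Rule A records an event dated week 16. Rule B records no confirmed progression at that point, and the patient's PFS time runs on to a later confirmed progression, death or censoring.

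Two conditions limit the comparison:

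1. The statement that any new lesion makes the visit PD stands in the site-investigator section. The SAP leaves further BICR detail to the Independent Review Charter, so how BICR codes a resolved new lesion cannot be read from these documents.
2. Patients with a single PD and no later scan count as progressed under either rule, so they do not contribute to the difference.

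**The case against.** The strongest reply is that the sections defining the variable, SAP 3.2.1.2 and protocol 11.1.3.2, ask only for confirmation at the next scheduled scan, which two consecutive PD responses satisfy. The worsening list sits among rules for managing treatment through progression, and Appendix F concerns investigator assessment. This would carry more weight if Section 3.1.2 did not itself name Section 3.1 as the source of its detail. As written, the SAP invokes the list and then departs from it.

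A second reply is that new lesions are handled elsewhere, in the BICR irRECIST 1.1 analyses, where they do not automatically mean PD. That is so, but those analyses are exploratory and use different criteria. Protocol Sections 3.1 and 3.2.3.4 limit them to 250 evaluable patients, and SAP 4.2.1.2 runs the PFS version on a BICR analysis set that Section 2.1 does not define. They do not settle which rule governs the RECIST 1.1 analysis.

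A third reply is that the stakes are modest. This stands. The analysis is supportive and outside the alpha structure, and a looser confirmation rule cannot turn a failed primary analysis into a positive one.

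A fourth is that the data for a stricter rule may be incomplete. This stands in part. SAP 3.1.1 names target-lesion changes among the BICR information but not new-lesion growth or graded non-target worsening, and SAP 3.1.3 says only that new lesions can be measured. Additional new lesions should be identifiable, since the SAP appendix lists exported new-lesion locations.

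**Conclusion.** The conflict is real and should be resolved. SAP 3.1.2 confirms new-lesion and non-target PD that persists without worsening; the criteria it cites do not. If the derivation is coded from BICR visit responses, the confirmation sensitivity analyses of PFS and ORR are weakened for those two patterns. The co-primary PFS analysis uses unmodified RECIST 1.1 and is unaffected.

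A reader might infer that new-lesion PD always confirms itself, so that the analysis cannot detect pseudo-progression at all. The documents do not support that. Even under the looser rule, target-lesion PD that falls back, non-target PD that reverts, and a new lesion that resolves and is read as non-PD all stay unconfirmed.

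A reader might also want a number of affected events or a shifted hazard ratio. That would need three quantities: the share of the 458 PFS events that are progressions, the share of those triggered by new or non-target lesions, and the share of those not worsening at the next scan, with the last two by arm for a hazard ratio. The documents give none of them. The size is therefore stated as two patterns in eight, which is not a proportion of patients, and the direction of any effect on the sensitivity hazard ratio is left open.

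The conclusion assumes that BICR reads a persisting new lesion, and persisting non-target PD, as PD again.

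**What to change.** State one governing rule and use it in both SAP 3.1.2 and 3.2.1.2.

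The preferred form applies the Section 3.1 criteria to the lesion records of the selected BICR reviewer: persistence for target-lesion PD; additional new lesions; and growth of the first new lesions where measurements exist. The SAP must also say what is done where worsening was not recorded, for example falling back on two consecutive PD visits and reporting by arm how many confirmations rest on that. Report PD at two consecutive visits as a separately labelled run, and carry the same pair of derivations through to ORR.

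If two consecutive PD responses are meant as the main rule, remove the cross-reference to the Section 3.1 criteria, list the departure in Table 9, and state how a resolved new lesion is coded.

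This concerns only the derivation of the analysis variable, not when treatment continues or stops. The cost is SAP wording and one extra derivation, with possibly somewhat fewer events in the sensitivity analysis.
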